[figure not shown]

## CLINICAL TRIAL PROTOCOL SYNOPSIS

Company name	Boehringer Ingelheim
Finished product name	Not applicable
Active ingredient name:	BI 409306
Protocol date	21 Aug 2017
Revision date	08 Nov 2017
Trial number	1289-0049
Title of trial:	A phase II randomised, double-blind, placebo-controlled study to evaluate the efficacy, safety, and tolerability of orally administered BI 409306 during a 28-week treatment period as adjunctive therapy to antipsychotic treatment for the prevention of relapse in patients with schizophrenia.
Coordinating Investigator:	 Phone:  Email: 
Trial site(s):	Multicentre trial
Clinical phase:	II
Objective(s):	To investigate the efficacy, safety and tolerability of BI 409306 25mg and 50mg once daily compared with placebo given for 28 weeks in patients with schizophrenia on antipsychotic treatment. The study is designed to show superiority of BI 409306 over placebo in preventing relapse of schizophrenia symptoms.
Methodology:	Multinational, multicentre, randomised, double-blind, placebo-controlled, parallel group study
Number of patients entered:	387
Number of patients on each treatment:	129 patients per treatment group
Diagnosis :	Patients with diagnosis of schizophrenia per International Statistical Classification of Diseases and Related Health Problems, 10 th Revision (ICD-10)
Main in- and exclusion criteria	Male and female patients 18-55 years old with schizophrenia in the stable phase of illness on a stable antipsychotic medication regimen. Patients can be treated with no more than two

	antipsychotic medications. Eligible patients will have experienced at least 2 relapses within the past 5 years or at least 1 relapse if they were diagnosed less than 3 years ago.																												
Test product(s):	BI 409306																												
dose:	
10 mg, 25 mg or 50 mg
 
During 28 week treatment period: 25 mg or 50 mg q.d.
 
During 7 day withdrawal/taper period during week 29 (10 mg tablets):
 
  
 	Treatment Group	
 
 25 mg q.d.	50 mg q.d.	
   
 Week 29	Day 1	20 mg	40 mg	
 
 Day 2	20 mg	30 mg	
 
 Day 3	20 mg	30 mg	
 
 Day 4	10 mg	20 mg	
 
 Day 5	10 mg	20 mg	
 
 Day 6	10 mg	10 mg	
 
 Day 7	10 mg	10 mg	
  
			Treatment Group		25 mg q.d.	50 mg q.d.	Week 29	Day 1	20 mg	40 mg	Day 2	20 mg	30 mg	Day 3	20 mg	30 mg	Day 4	10 mg	20 mg	Day 5	10 mg	20 mg	Day 6	10 mg	10 mg	Day 7	10 mg	10 mg
				Treatment Group																									
		25 mg q.d.	50 mg q.d.																										
Week 29	Day 1	20 mg	40 mg																										
	Day 2	20 mg	30 mg																										
	Day 3	20 mg	30 mg																										
	Day 4	10 mg	20 mg																										
	Day 5	10 mg	20 mg																										
	Day 6	10 mg	10 mg																										
	Day 7	10 mg	10 mg																										
mode of administration:	p.o. (oral)																												
Comparator products:	Matching placebo																												
dose:	Not applicable																												
mode of administration:	p.o.																												
Duration of treatment:	28 weeks																												
Endpoints	
Primary efficacy endpoint:
 
The primary endpoint is time to first relapse until study end (planned at 28 weeks). Time of relapse will be obtained by selecting the earliest date from any, or all of the following 6 criteria:
 
 
• Time to hospitalization (involuntary or voluntary admission), intensive outpatient therapy or use of home treatment, as an alternative to hospitalization, for decompensation of schizophrenia symptoms
 
• Time to an assessment on the Clinical Global Impressions - Severity (CGI-S) of <math>\geq 5</math> (markedly ill) and either:             
 
- an increase on any of the following individual Positive and Negative Syndrome Scale (PANSS) items: conceptual disorganization, hallucinatory behavior, suspiciousness, unusual thought content - to a score <math>> 4</math> with an absolute increase of <math>\geq 2</math> on that specific item since randomisation
 
 
 
 
or
																												

	
 
- an increase on any of the following individual PANSS items: conceptual disorganization, hallucinatory behavior, suspiciousness, unusual thought content -to a score > 4 and an absolute increase of <math>\geq 4</math> on the combined 4 PANSS items since randomisation
 
 
or
 
 
- PANSS total score increase of <math>\geq 25\%</math> relative to baseline score or an increase of <math>\geq 10</math> points if baseline score was <math>\leq 40</math>
 
 
 
• Time to a prescription for a new antipsychotic or time to an increase in dose of an ongoing antipsychotic medication for significant worsening of schizophrenia symptoms
 
• Time to clinically significant homicidal ideation, in the investigator's judgement
 
• Time to suicidal behavior, or time to assessment of suicidal ideation type 4 or 5 on the Columbia Suicide Severity Rating Scale (C-SSRS)
 
• Time to deliberate self-injury and/or violent behaviour resulting in suicide or in clinically significant injury to the patient or another person or property damage, in the investigator's judgement
 
 
Secondary efficacy endpoints:  Key secondary endpoint:
 
 
• Change from baseline in Positive and Negative Symptom Score (PANSS) positive symptoms score after 28 weeks of treatment.
 
•
 
 
Secondary endpoints:
 
 
• Time to new prescription or increase in dose of an ongoing antipsychotic medication.
 
• Change from baseline in Clinical Global Impressions–Severity (CGI-S) scale score after 28 weeks of treatment.
 
• Patient Global Impressions-Improvement (PGI-I) scale score after 28 weeks of treatment.
 
• Suicidal ideation and behaviour as assessed by C-SSRS after 28 weeks of treatment.
 
• Change from baseline in Personal and Social Performance scale (PSP) score after 28 weeks of treatment.
 

Safety criteria:	Physical examination, vital signs, laboratory tests, electrocardiogram (ECG), suicidality, extrapyramidal symptoms, and occurrence of serious and non-serious adverse events will be assessed.
Statistical methods:	For the primary endpoint of time to relapse, the equality of the hazard rates will be tested by the Wald test for the treatment effect in a stratified Cox proportional hazards model. The model includes treatment as the only covariate and is stratified by country.

	Secondary endpoints will be analysed descriptively using relative risk ratios and 95% confidence intervals.
--	---

**FLOW CHART**

Trial Periods	Screening Period 	Randomized Treatment Period															Withdrawal/Taper 			Completed Patients		Early D/C Patients			All Patients	
		2	3	4	5	6	7	8	9	10	11	12	13	14	15	16	17	18	19	EOT 	F/U 	Follow-up	Early D/C Option 1	Early D/C Options 2-4		End of Study
Visit	1	2	3	4	5	6	7	8	9	10	11	12	13	14	15	16	17	18	19	EOT 	F/U 	EOT 	EOT 	F/U 		
Study week	-4	2	4	6	8	10	12	14	16	18	20	22	24	26	28	29	32									
Study day	-28	1	15	29	43	57	71	85	99	113	127	141	155	169	183	197	V16+2	V16+4	V16+7	V16+28	EOT +28 days					
Visit window in days	-28 to -7	N/A	+/-3	+/-3	+/-3	+/-3	+/-3	+/-3	+/-3	+/-3	+/-3	+/-3	+/-3	+/-3	+/-3	+/-3	+/-1	+/-1	+/-1	+/-3	+/-3					
Informed consent 	X																									
Demographics	X																									
Medical history	X																									
Physical examination	X																X								X	
Vital signs	X	X		X		X		X		X		X		X		X	X	X	X		X	X	X	X	X	X
Height	X																									
Weight	X							X								X					X	X	X	X	X	
Pregnancy test (urine; females only) 	X	X		X		X		X		X		X		X		X			X						X	
12 lead-ECG 	X							X								X									X	
Safety laboratory tests (urine/blood) 	X	X						X				X				X			X		X	X	X	X	X	
Antipsychotic medication assessment in plasma 	X							X				X				X									X	
Pharmacokinetic sampling (BI 409306) 		X						X								X										
Urine drug screen	X																									
Pharmacogenomic sampling 	X	X																								
Optional DNA biobanking (requires separate ICF) 		X																								
Mini-international neuropsychiatric interview (M.I.N.I.)	X																									
In-/Exclusion Criteria	X	X																								
Randomization		X																								
Phone Visit 			X		X		X		X		X		X		X											

**FLOW CHART (Cont.)**

Trial Periods	Screening Period 	Randomized Treatment Period																Withdrawal/ Taper 			Completed Patients		Early D/C Patients			All Patients
																		Follow-up		Early D/C Option 1	Early D/C Options 2-4	F/U 	End of Study			
		2	3	4	5	6	7	8	9	10	11	12	13	14	15	16	17	18	19					EOT 	F/U 	
Visit	1	2	3	4	5	6	7	8	9	10	11	12	13	14	15	16	17	18	19	EOT 	F/U 	EOT 	EOT 	F/U 	End of Study	
Study week	-4		2	4	6	8	10	12	14	16	18	20	22	24	26	28					29	32				
Study day	-28	1	15	29	43	57	71	85	99	113	127	141	155	169	183	197	V16+2	V16+4	V16+7		V16+28				EOT +28 days	
Visit window in days	-28 to -7	N/A	+/-3	+/-3	+/-3	+/-3	+/-3	+/-3	+/-3	+/-3	+/-3	+/-3	+/-3	+/-3	+/-3	+/-3	+/-1	+/-1	+/-1		+/-3			+/-3		
Clinical Global Impressions -Severity (CGI-S)	X	X		X		X		X		X		X		X		X							X			
Clinical Global Impressions-Improvement (CGI-I)												X				X							X			
Patient Global Impressions –Improvement (PGI-I)												X				X							X			
Personal and Social Performance scale (PSP)		X														X							X			
Positive and Negative Syndrome Scale (PANSS)	X	X		X		X		X		X		X		X		X				X	X	X	X			
Columbia Suicide Severity Rating Scale (C-SSRS)	X	X	X	X	X	X	X	X	X	X	X	X	X	X	X	X	X	X	X		X	X	X	X		
Interactive Response Technology (IRT) Use 	X	X		X		X		X		X		X		X		X				X		X	X			
Dispense study drug		X		X		X		X		X		X		X		X 										
Smartphone app training, set-up/ In-clinic drug administration		X																								
Adverse events	X	X	X	X	X	X	X	X	X	X	X	X	X	X	X	X	X	X	X		X	X	X	X		
Concomitant therapy	X	X	X	X	X	X	X	X	X	X	X	X	X	X	X	X	X	X	X		X	X	X	X		
Compliance check			X	X	X	X	X	X	X	X	X	X	X	X	X	X	X	X	X			X	X			
Termination of trial medication																				X		X	X			
Trial Completion																								X		
Vital Status 																								X		

1. Screening Visit procedures are not required to be completed on the same day.
2. Patients will be randomised to either abrupt withdrawal or slow taper of study drug for 7 days. Vital signs, suicidality and adverse events will be closely monitored during this period.
3. End of Treatment (EOT) for patients who complete the treatment and withdrawal/taper periods will be completed at Visit 19. Patients who discontinue study drug prematurely should ideally be observed until study end as if they were still receiving blinded study treatment. There are 4 options for observing patients after premature drug discontinuation. Sections [3.3.4.1](#) and [6.2.2](#) and [6.2.2.1](#) provide additional information.  
Early Discontinuation (D/C) Option 1: An EOT Visit must be conducted within 7 days of the last dose of study medication for patients who agree to conduct regularly scheduled visits after premature drug discontinuation. Thereafter, patients should be followed up according to the regular visit schedule. Visit 16 will be the final visit for patients choosing this Early D/C Option.  
Early D/C Options 2-4: An EOT Visit must be conducted within 7 days of the last dose of study medication for patients who agree to conduct the remaining visits over the phone, or patients who agree to be contacted or data collected via alternative sources approximately 28 weeks after the patient was randomised.
4. Patients who complete the treatment and withdrawal/taper periods will be scheduled for a Follow-Up Visit 28 days after Visit 16. Patients who enter the withdrawal/taper period, but discontinue taking their study drug will have a Follow-up Visit as planned at Week 32.
5. Patients who prematurely discontinue study medication and choose Early D/C Option 1 do not need a Follow-Up Visit if they discontinued >4 weeks prior to Visit 16. If a patient choosing Early D/C Option 1 discontinues <4 weeks prior to Visit 16, a Follow-up Visit will be performed 28 days after the EOT Visit. Patients who prematurely discontinue study medication and choose Early D/C Options 2-4 will have a Follow-Up Visit performed 28 days after the EOT visit. See Sections [3.3.4.1](#), [6.2.2](#), and [6.2.2.1](#).
6. Written informed consents for main study and optional pharmacogenomics test for deoxyribonucleic acid (DNA) banking must be obtained before any study-related procedures and assessments are performed. The registration of patients for the study is through the Interactive Response Technology (IRT). Re-consenting may become necessary when new relevant information becomes available and should be conducted according to the sponsor's and Institutional Review Board (IRB)/ Independent Ethics Committee's (IEC) instructions.
7. Female patients of childbearing potential must perform urine (dipstick) pregnancy test at Visits 1 through EOT.
8. A 12-lead electrocardiogram (ECG) is to be performed during the scheduled visits or within 24 hours prior to the visit, except for Visit 1 (Screening Visit), where the ECG test will be performed only after a written informed consent for the main study has been obtained.
9. Routine laboratory tests are hematology, chemistry, coagulation, and urinalysis as described in [Table 5.2.3:1](#). Patients should be fasting for at least 8 hours prior to blood samples collection, except at Visit 1.
10. Blood samples will be collected to check the presence of antipsychotic medication(s) in plasma. A sample should also be collected at the time a relapse is diagnosed.
11. Pharmacokinetic samples will be collected to measure BI 409306 and its two metabolites CD 13896 and CD 14084. See Sections [5.3](#) and [10.1](#) for details.
12. One blood sample will be taken at screening visit for genotyping of CYP2C19 from all patients taking medication known to be strong or moderate inhibitors of CYP1A2. One additional blood sample for genotyping of genes involved in absorption, distribution, metabolism and elimination will be collected preferably at Visit 2. However, collection of this sample at later visits is permitted.
13. Collection of a sample for DNA biobanking is optional (See [Section 5.4.1](#) for more details). Participating patients are required to give informed consent specifically for biobanking. DNA biobanking requires only one blood sample to be taken, preferably at Visit 2 (Randomisation). However, collection at later visits is permitted as long as the informed consent for biobanking remains valid.
14. Interim phone visits are scheduled to assess the overall status of the patient, check compliance, and to collect new AE and concomitant medication information. If symptom worsening is suspected, an unscheduled in-clinic visit should be scheduled. See [Section 6.2.2](#). Columns are shaded in grey in the [Flow Chart](#) to indicate phone visits.
15. The study staff must utilize the Interactive Response Technology (IRT) for entering the patient into the system for screening, randomisation, and study medication allocation and tracking.
16. Patients who complete the 28 week treatment period will be dispensed a one-week wallet for the withdrawal/taper period.
17. Patients who have prematurely discontinued study drug and have not continued making regular visits (in person or phone) must have Vital Status collected approximately 28 weeks after the patient was randomised.

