#### **3.3.4.1 Withdrawal from trial treatment**

An individual patient is to be withdrawn from trial treatment if:

- The patient wants to withdraw from trial treatment, without the need to justify the decision.
- The patient becomes pregnant during the trial. Patient will be followed up until birth or other termination of the pregnancy.
- The patient needs to take concomitant drugs that in the clinical judgment of the investigator interfere with the investigational product.
- The patient can no longer be treated with trial medication for other medical reasons (such as surgery, adverse events, other diseases, or pregnancy)
- The patient has repeatedly shown to be non-compliant with important trial procedures and, in the opinion of both the investigator and sponsor representative, is not willing or able to stick to the trial requirements in the future.

Every effort should be made by the site staff to encourage patients to remain in the study and on study drug if medically safe. Patients who prematurely discontinue study drug must complete the End of Treatment (EOT) procedures as described in the [Flow Chart](#) and Sections [6.2.2](#) and [6.2.3](#). Patients who discontinue study drug prematurely should ideally be observed until the end of the trial as if they were still receiving blinded study treatment. For all patients the reason for withdrawal from trial treatment (e.g. adverse events) must be recorded in the CRF. These data will be included in the trial database and reported.

Patients that are not actively taking study drug may be less motivated to adhere to the study visit schedule. Investigators and site staff should work to detect early signs of waning interest and readily present such patients with the following options to encourage continued participation:

Early D/C Option 1:	Continue to conduct regularly scheduled study visits.
Early D/C Option 2:	Conduct all remaining study visits over the phone. At the time of planned clinic visits, only the following assessments need to be conducted via phone: PANSS, CGI-S, C-SSRS, Adverse Events, Concomitant Therapy.
Early D/C Option 3:	Discontinue participation in remaining study activities but permit collection of the occurrence of psychiatric illness/relapse and vital status approximately 28 weeks after randomisation through the patient or alternative person designated by the patient (e.g., family, spouse, partner, legal representative, or physician).

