Early D/C Option 4:	Same as Option 3 above, but with the possibility of collection of the occurrence of psychiatric illness/relapse and vital status approximately 28 weeks after randomisation through review of patient's medical information from alternative sources (e.g., doctor's notes, hospital records, etc.).

Patients will be asked to choose the most rigorous form of follow-up that they are willing to comply with. Patients who refuse all four of the above are considered to have fully withdrawn consent to participate in the study.

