### 6.2 DETAILS OF TRIAL PROCEDURES AT SELECTED VISITS

Study procedures to be performed at each visit are listed in the [Flow Chart](#). Additional details regarding visit procedures are provided in [Section 5](#) and below.

The members of the site staff that will be administering the assessments have to be properly trained (either at the investigator meeting or individually), and training documentation must be filed in the ISF. It is the responsibility of the Principal Investigator at the site to ensure proper training of all members of the site staff involved in the assessments.

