### Patients prematurely discontinuing study drug:

Patients who discontinue study drug prematurely should ideally be observed until study end as if they were still receiving blinded study treatment. There are 4 Options for observing patients after premature drug discontinuation. See [Section 3.3.4.1](#)

**Early D/C Option 1:** For patients who prematurely discontinue taking study drug who are willing to conduct the remaining visits, the following should be performed:

- EOT Visit must be performed within 7 days of last intake of study drug, or as soon as possible.
- Thereafter, patients should be followed up according to the regular visit schedule through Visit 16.
- A Follow-Up Visit is not necessary if the patient discontinued >4 weeks prior to Visit 16. If a patient discontinues <4 weeks prior to Visit 16, a Follow-up Visit will be performed 28 days after the EOT Visit.

**Early D/C Option 2:** For patients who prematurely discontinue taking study drug who are willing to conduct the remaining visits over the phone, the following should be performed:

- EOT Visit must be performed within 7 days of last intake of study drug, or as soon as possible.
- A Follow-up Visit will be performed 28 days after the EOT Visit.
- Thereafter, patients should be followed up over the phone according to the regular visit schedule through Visit 16. See [Section 3.3.4.1](#) for Early D/C Option 2 which details the assessments to be conducted via phone.

**Early D/C Options 3 and 4:** For patients who prematurely discontinue study drug and agree to be contacted or have information collected from an alternative source at the end of the study, the following should be performed:

- EOT Visit must be performed within 7 days of last intake of study drug, or as soon as possible.
- A Follow-up visit will be performed 28 days after the EOT Visit.
- Occurrence of psychiatric illness/relapse and vital status must be collected approximately 28 weeks after the patient was randomised.

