- Patients who chose Early Discontinuation Option 5, i.e. withdrew consent per CTP (for ITT and Full FU analysis): Events (relapses) are counted in the time to event analysis whenever they occur between the first dose of randomized treatment and the patient's date of consent withdrawal.
 - Patients with event counted: <date of event> <date of first drug administration> +1
 - Patients without event counted: <date of consent withdrawal> <date of first drug administration >+1 day
- Patients who are Lost-to-Follow-up (for ITT analysis): Events (relapses) are counted in the time to event analysis whenever they occur between the first dose of randomized treatment and the last at-risk date.

- Patients with event counted: <date of event> <date of first drug administration> +1 day
- Patients without event counted: <date of last at-risk> <date of first drug administration >+1 day

*Please note: Patients who are LTFU during the study (regardless of initial Early Discontinuation choice), but were successfully found towards the end of study via a vital status call, will be included in the Full-FU analysis period by replacing as follows:

• Patients without event counted: <date of vital status/date of EOS> – <date of first drug administration >+1 day

The following SAS code will be used:

```
proc phreg data= primary;
   CLASS &trt.(ref="Placebo") / order=internal;
   model aval*cnsr(1) = &trt./ties=breslow;
   strata countrdc;
   hazardratio 'HR' &trt. /diff=ref cl=both;
run;
```

Subgroup analyses will be performed on the subgroups specified in Section 6.4. Definition of Japanese patients is provided in Section 9.1. The same model as described above for the primary efficacy analysis, will be used for these analyses.

The following SAS code will be used for survival plot:

```
proc lifetest data=primary method=km plots=survival(failure test
atrisk);
time aval*cnsr(1);
id usubjid;
strata &trt. /test=logrank;
run;
```

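### Flow chart footnote 17 sets no week-28 relapse query for patients who chose Option 1 or 2 and then stopped visits, and the SAP can count their vital status call as relapse-free time

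*Protocol*

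**What the plan says.** **Flow chart.** The only row for the week-28 contact is Vital Status. Its footnote 17 says that patients who stopped study drug early and "have not continued making regular visits (in person or phone) must have Vital Status collected approximately 28 weeks after the patient was randomised". The group is defined by behaviour (off drug, no visits), not by the option chosen. Protocol 6.2 opens with "Study procedures to be performed at each visit are listed in the" flow chart, and adds that further details follow in Section 5 and in the text below it.

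**Options 3 and 4.** Protocol 3.3.4.1 describes Option 3 patients as ending other study activities but agreeing to "permit collection of the occurrence of psychiatric illness/relapse and vital status approximately 28 weeks after randomisation". Option 4 adds "collection of the occurrence of psychiatric illness/relapse and vital status approximately 28 weeks after randomisation through review of patient's medical information". Section 6.2.2 makes this mandatory for both: "Occurrence of psychiatric illness/relapse and vital status must be collected approximately 28 weeks after the patient was randomised".

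**Options 1 and 2.** Option 1 patients keep the regular visits. For Option 2, at planned clinic visits, "only the following assessments need to be conducted via phone: PANSS, CGI-S, C-SSRS, Adverse Events, Concomitant Therapy". Section 6.2.2 has both groups followed on the regular schedule through Visit 16. It does not say what is asked at week 28 if they stop before then.

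**SAP 7.4.1.** Lost patients without an event are censored in the ITT analysis at the last at-risk date. A note adds that patients lost during the study, regardless of their first choice of option, "but were successfully found towards the end of study via a vital status call, will be included in the Full-FU analysis period". The replacement formula covers only patients without an event and runs to the date of vital status or end of study.

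**Protocol 7.3.1.** If relapse cannot be determined between discontinuation and last contact, no relapse is assumed.

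**The concern.** Relapse is the primary endpoint, and the week-28 contact is the last chance to learn about it for patients who have stopped attending. If the form for that contact records only whether the patient is alive, a patient who relapsed after leaving looks the same as one who did not.

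Two things follow. In the Full follow-up analysis, which is the protocol's sensitivity analysis for the primary result, the patient gains event-free time that nobody verified. In the ITT analysis the patient is censored when contact was lost, although the trial spoke to the patient, or about the patient, near the end of the 28 weeks. A sensitivity analysis meant to test robustness would then rest partly on an assumption of no relapse.

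The missing date is a related gap. Every rule in SAP 7.4.1 for a patient with an event starts from the event date, but the week-28 items in 3.3.4.1 and 6.2.2 ask only whether relapse occurred.

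**Working it through.** **Passages side by side, by patient group**

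| Patient off drug | Relapse asked at about week 28? | SAP 7.4.1 if no event is recorded |
|---|---|---|
| Option 1 or 2, still visiting or phoning | Yes, through the scheduled assessments to Visit 16 | End of study date |
| Option 3 or 4 | Yes, mandatory (3.3.4.1, 6.2.2), occurrence only | End of study date if follow-up is completed |
| Option 1 or 2, then stopped visits | Not stated; footnote 17 asks for vital status | ITT: last at-risk date. Full follow-up: vital status or end of study date if found |
| Refused all four options | No; consent withdrawn | Date of consent withdrawal |

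The gap is the third row.

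**What the rules do to one such patient (illustration).** Suppose the last contact is Visit 8 (Day 85), the patient relapses afterwards, and a call on Day 197 establishes only that the patient is alive.

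- ITT: censored at 85 days.
- Full follow-up: event-free for 197 days, so 197 − 85 = 112 days of relapse-free time are added for a patient who relapsed.

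The last at-risk date includes phone contacts at which the patient was reached. The SAP does not say whether the vital status call is one of these. Because it gives a separate replacement for Full follow-up only, the natural reading is that the call does not enter the ITT analysis.

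**Size: the plan's figures first.** Inputs from Protocol 7.7: two-sided alpha 0.05, power 80%, HR 0.50, placebo relapse 30%, dropout 20%, 258 active and 129 placebo.

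- Events = (1.960 + 0.842)² / [(1/3)(2/3)(ln 0.5)²] = 73.5, rounded up to 74, as stated.
- Sample size, with relapse hazards 0.3567 (= −ln 0.70) and 0.1783, dropout hazard 0.2231 (= −ln 0.80), and event probability λ/(λ+γ) × [1 − exp(−(λ+γ))]: 0.271 on placebo, 0.147 on active, 0.188 on average. 73.5 / 0.188 gives 390.7 with unrounded inputs, against 385 stated, which is within 3%.

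This calculation gives dropouts no events after they leave, so the planned sample size already allows for losing them.

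**A ceiling only.** Early stoppers: 129 × 0.20 = 25.8 and 258 × 0.20 = 51.6, together about 77. With stop times spread evenly, the mean chance of relapse in the remaining time is 1 − (1 − e^(−λ))/λ.

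- Placebo: 1 − 0.30/0.3567 = 0.159.
- Active, effect persisting: 1 − 0.1633/0.1783 = 0.084. Effect lost at stopping: 0.159.
- Relapses after stopping: 25.8 × 0.159 + 51.6 × 0.084 = 8.4, or 77.4 × 0.159 = 12.3.

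These 8 to 12 relapses would fall in the gap only if every early stopper had chosen Option 1 or 2 and stopped visits at once. Patients in the first two rows of the table must be removed, and the documents give no split. SAP Section 4 also says recruitment stopped early, so figures based on 387 are design figures.

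**The case against.** A reader might infer that the trial reaches its dropouts at week 28 and asks all of them only whether they are alive. The documents do not support that. Footnote 17 requires vital status but does not say that nothing else is asked. For Options 3 and 4, Section 6.2.2 requires relapse occurrence at the same contact. The flow chart is not self-contained either: its footnote 3 describes "patients who agree to be contacted or data collected via alternative sources approximately 28 weeks after the patient was randomised" and sends the reader to Sections 3.3.4.1 and 6.2.2.

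For the remaining group the defence has several parts.

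- Sections 7.3.1 and 7.5 promise follow-up for relapse without regard to option. This states an intention; 7.5 points back to 3.3.4.1, which has no week-28 query for Options 1 and 2.
- Staff are told to watch for waning interest and present the options, so a fading patient may move to Option 3 or 4. This shrinks the group but does not empty it: the SAP note provides for lost patients whatever they first chose.
- The SAP note does not say that relapse goes unasked at the call. True, but it does not require the question, and it gives a replacement rule only for patients without an event.
- Worsening of the underlying disease is an adverse event (5.2.6.2), its onset date is mandatory (8.3.1), and SAP 6.6 imputes missing dates for events that meet the endpoint. This may supply some dates, provided the site learns of the event.
- Planned dropout already allows for lost events. This stands, and it is why no power shortfall is claimed.

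**Conclusion.** The point holds in a limited form. For patients who chose Option 1 or 2 and then stopped visits, no section sets a week-28 relapse query. Following the SAP as written, a vital status answer can extend their relapse-free time in the Full follow-up analysis, while the ITT analysis makes no stated use of the contact. The missing relapse date is a second, smaller gap that also touches Options 3 and 4.

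The number affected cannot be derived. It is below the 77 or so early stoppers, and 8 to 12 relapses is a ceiling that rests on 20% dropout, even stop times, 30% placebo relapse and HR 0.50.

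Two further inferences should be resisted. The documents do not show that these patients relapse more often than others. Nor does unequal stopping between arms by itself bias the hazard ratio: that would also need censoring related to relapse risk, which is plausible but not shown. This is an inexpensive improvement to data collection and derivation, not evidence that the primary analysis is invalid.

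**What to change.** 1. Flow chart: change the Vital Status row and footnote 17 to relapse status (occurrence, date, and which criterion of Section 2.1.2 was met) and vital status. Apply this to every consenting patient no longer making regular visits, whatever option was first chosen, with the question covering the time up to the planned Day 197.
2. Protocol 3.3.4.1 and 6.2.2: use the same wording, so that date and criterion are also asked under Options 3 and 4.
3. SAP 7.4.1: use the dated answers in both the ITT and Full follow-up derivations. Add a rule for found patients with an event. Extend event-free time to the call date only when relapse status was actually obtained; otherwise keep the last at-risk date, and state that a call yielding vital status alone does not move it.

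The cost is wording and a few eCRF fields on a contact already planned. The downside is that relapse dates will rest on recall or on records, so the source of each date should be recorded.
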